A Study to Evaluate the Feasibility of Robotic
Bronchoscopy-guided Miniature Cryoprobe
Biopsy of Peripheral Pulmonary Lesions

NCT05399082

December 15, 2021

A study to evaluate the feasibility robotic bronchoscopy guided miniature cryoprobe biopsy of peripheral pulmonary lesions

Principal Investigator: [name] MD

Site(s) where study will be performed:

Mayo Clinic, Rochester, MN

1 Objectives

1.1 Primary Objective:

This is a prospective randomized control study to evaluate the feasibility of using a miniature (1.1 mm) cryoprobe to perform biopsy of peripheral pulmonary lesions using robotic bronchoscopy

1.2 Secondary Objective:

1. To assess safety of cryobiopsy through a robotic bronchoscope
2. Comparison of sample size acquired via cryobiopsy to routine forceps biopsy.
3. Comparison of quality of sample for histologic diagnosis of malignant lung lesions between cryobiopsy to routine forceps biopsy.

2 Background

Lung nodules and masses may represent primary lung cancer, metastatic disease, infection, or more benign findings such as granuloma. Often, lung nodules require biopsy to confirm a diagnosis.

Computerized tomography (CT) guided lung biopsy is the gold standard technique. Diagnostic rates are 90% or greater with excellent pathologic quality core biopsies. However, CT guided core lung biopsy is associated with a high pneumothorax rate that may be as high as 20%(1). Because of this, there has been intense interest in bronchoscopic alternatives to obtain biopsies while minimizing the risk of pneumothorax. Patients suspected of having lung cancer undergo bronchoscopy for mediastinal staging with lymph node sampling. Mayo Clinic has acquired the Ion Robot bronchoscopy system (Intuitive Surgical, Sunnyvale, CA, USA). This system uses a robotically driven 3.5 mm steerable catheter to navigate into the periphery of the lung. A 2.0 mm working channel allows the passage of needles, up to

19 gauge, and forceps to obtain biopsy specimens. Using this method, diagnostic yields are comparable to CT biopsy with a pneumothorax rate less than 2%. However, these biopsy specimens often lack adequate tissue for both diagnosis and molecular adequacy that can be obtained with CT biopsy using core needles.

Cryobiopsies are obtained with cryoprobes which are flexible catheters that can be passed through the channel of a bronchoscope. Rapid cooling of tissue results from the Joule-Thomson effect which causes tissue to freeze and adhere to the probe. The biopsy is obtained by subsequently avulsing small fragments of tissue. This results in larger specimens with less crush artifact. This is a common technique used at centers around the world to obtain lung biopsies. Mayo Clinic has significant published experience with this technique (1-3). This technique has not been combined with robotic bronchoscopy due to size (both length and diameter) of older generation cryoprobes.

Erbe Medical, (Marietta, GA, USA) recently received FDA approval for a 1.1mm disposable cryoprobe, which will pass through the working channel of the Ion Robotic bronchoscope. The goal of this study is to assess the feasibility of using that probe with the Ion Robot and evaluate biopsy quality.

3 Research plan and method

Study design: This will be a prospective pilot study.

We will include patients who undergo robotic bronchoscopy with cryobiopsy at Mayo Clinic, Rochester, MN who meet the below inclusion/exclusion criteria.

4 Inclusion Criteria/exclusion criteria

4.1 Inclusion criteria:

1. Male and female patients age ≥ 18 at the time of informed consent
2. Patients clinically meets indication for peripheral lung nodule biopsy and has been scheduled for robotic bronchoscopy

Lesion Criteria:

Inclusion:

1. Pulmonary nodules of 8-50mm in largest dimension

4.2 Exclusion Criteria:

1. Patients with known bleeding diathesis
2. Platelet count <50,000 per μL
3. Current use of systemic anticoagulation or antiplatelet therapy without the ability to hold therapy for the recommended amount of time prior to an invasive procedure (aspirin monotherapy is acceptable)
4. Inability or unwillingness to give informed consent
5. Pregnant or nursing females, or females of child-bearing potential who decline a pregnancy test prior to enrollment
6. Pulmonary hypertension, defined as a right ventricular systolic pressure > 50 mmHg
7. Individuals with current or recent systematic conditions, such as, acute kidney injury, or conditions that would mandate anticoagulation, such as a recent coronary stent.
8. International Normalized Ratio (INR) <1.5
9. Do Not Resuscitate (DNR) status
10. Do Not Intubate (DNI) status

5 Specific aims:

Primary Objective:

This is a prospective randomized control study to evaluate the feasibility of using a miniature (1.1 mm) cryoprobe to perform biopsy of peripheral pulmonary lesions using robotic bronchoscopy

Secondary Objectives:

1. To assess safety of cryobiopsy through a robotic bronchoscope
2. Comparison of sample size acquired via cryobiopsy to routine forceps biopsy.
3. Comparison of quality of sample for histologic diagnosis of malignant lung lesions between cryobiopsy to routine forceps biopsy.

6 Study Endpoints:

6.1 Primary Endpoint:

Feasibility of obtaining biopsy will be assessed as the ability to insert the cryoprobe into the robotic working channel and retrieve at least one tissue sample per patient that is considered by the bronchoscopist as adequate for further pathological analysis.

6.2 Secondary Endpoints:

Procedural:

1. Duration of each individual biopsy procedure from first insertion of probe into robotic sheath to removal of specimen. Duration of full procedure from first insertion of probe into robotic sheath to last removal of specimen.
2. Freezing time (seconds) for cryoprobe biopsies
3. Number of “successful” and “unsuccessful” biopsy attempts.

One attempt is defined as insertion of the biopsy probe into the robotic sheath, activation/employment of the biopsy mechanism at the target site and retrieval via the robotic sheath. A biopsy attempt is successful if a tissue sample that is considered by the bronchoscopist to be adequate for further pathological analysis can be retrieved. In the case of unsuccessful cryobiopsy attempts, it should be recorded whether tissue sampling was successful but the tissue sample was “lost” i.e. if a successful “bite” took place as indicated by freezing activation and adhesion, but the sample detached from the cryoprobe tip on its way out of the body and could not be recovered (e.g. because it was too big to fit thorough the over sheath or tissue channel or freezing was deactivated too soon).

Histological:

4. Histological accessibility grade

Assessed by pathologist according the following scale:

Grade	Pathological Description
1	Insufficient tissue
2	Sizable tissue sample but no diagnostic material (likely indicating the lesion was missed but a reasonable amount of tissue was sampled)
3	Lesional tissue present but considerable artifact clearly hampering the morphologic evaluation of the lesion (diffuse crush artifact, procedure-related hemorrhage, large amount of necrosis)
4	Diagnostic material

5. Histological diagnostic yield

Defined as the ability of the pathologist to make a diagnostic statement based on the histological analysis of the obtained tissue samples.

6. Total histological area (mm²)

7. Crush artifacts (% total area)

8. Fresh hemorrhage (procedural related) (% total area)

9. Other artifacts that obscure pathological assessment (% total area, artifacts will be listed)

10. Different tissue types in the tissue specimen (e.g. alveoli, bronchus, mucus, blood, target tissue; % total area) .

Safety:

11. Occurrence and grading of bleeding according to CTCAE (version 5) following each individual biopsy and overall for each procedure.

12. Occurrence and grading of the following related adverse events according to CTCAE (version 5):

a. Pneumothorax, as determine by post procedural chest x-ray, which is standard of care after robotic bronchoscopy, or any intraprocedural imaging such as cone beam CT or fluoroscopy.

b. Respiratory failure

13. Occurrence of all related adverse events Grade 3-4 (according to CTCAE) during or directly following the biopsy procedure.

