7 DSMB

The Department of Surgery DSMB will provide interim reviews and serve as in internal safety control.

8 Early Stopping Rules

If any patient is permanently disabled, has life threatening consequences (defined as Grade 3 bleeding episode or Grade 4 adverse event by CTCAE Version 5.0) the study will be temporarily halted until the DSMB has reviewed the Adverse Events. The study will be continued if the event is demonstrably unrelated to the procedure or was a reasonable adverse event in relation to the research study procedure. The trial will be permanently halted for a grade 5 event (death) if attributable to the cryobiopsy procedure. The study will be continued if the event is demonstrably unrelated to the procedure or was a reasonable adverse event in relation to the research study procedure.

9 Study Plan:

The proposed study will prospectively enroll patients being evaluated for robotic bronchoscopic lung nodule/mass biopsy which will be done as **part of their standard medical care**.

1. Patients who present for robotic navigational bronchoscopy with planned biopsy of lung nodule or mass will be eligible to consent to be included in prospective study.
2. Patients will be screened for inclusion and exclusion criteria via review of medical history and standard of care pre-procedure examinations.
3. Robotic assisted bronchoscopy will be performed as per institutional standard of care. In addition to robotic shape sensing technology, radial probe ultrasound, fluoroscopy, and cone beam CT may be used for navigation.
4. The position of the navigation catheter relative to the nodule or mass will be confirmed via radial EBUS and cone beam CT.
5. The lung nodule or mass will be biopsied using standard biopsy needles, ranging from 19-23 gauge. Rapid onsite evaluation of the needle biopsy will be performed according to standard of care.
6. Per clinical practice, after the needle biopsy we will also take tissue biopsies. We will take 3 biopsies using the 1.1 mm Erbe cryoprobe and 3 biopsies using forceps. The order in which the biopsy methods are employed will be randomized 1:1. In 50% of the patients, forceps will be

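### Exclusion criterion 8 has the INR limit the wrong way round: it bars INR below 1.5 and sets no upper limit

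*Combined protocol and SAP*

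**What the plan says.** Section 3 of the combined protocol and SAP makes the criteria in section 4 govern who is included. In section 4.2, the exclusion list, item 8 reads "International Normalized Ratio (INR) <1.5".

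Four other items in that list concern bleeding risk:

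- Item 1: "Patients with known bleeding diathesis".
- Item 2: "Platelet count <50,000 per" microlitre.
- Item 3: "Current use of systemic anticoagulation or antiplatelet therapy without the ability to hold therapy" for the recommended period before an invasive procedure.
- Item 7, in part: "conditions that would mandate anticoagulation, such as a recent coronary stent".

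Section 9, step 2 puts the list into use: "Patients will be screened for inclusion and exclusion criteria via review of medical history and standard of care pre-procedure examinations". Section 12 schedules the eligibility review at the screening visit and again at the procedure visit. It lists no coagulation test.

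Bleeding is a safety outcome. Section 6.2, item 11 records "Occurrence and grading of bleeding according to CTCAE (version 5) following each individual biopsy and overall for each procedure". Section 8 temporarily halts the study for life-threatening consequences, "defined as Grade 3 bleeding episode or Grade 4 adverse event by CTCAE Version 5.0".

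**The concern.** A higher INR means slower clotting, so an exclusion meant to protect patients from biopsy bleeding should remove high values. Item 8 removes low ones. Patients with unremarkable coagulation are shut out, and no numeric ceiling applies to anyone else.

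Two things are at stake. The first is safety: a patient with a raised INR that is not recognised as a bleeding diathesis, and is not tied to a drug or condition under items 3 or 7, meets no written exclusion. The second is valid eligibility: staff who ignore the printed sign and apply the sensible rule enrol patients who meet a written exclusion. In both cases it becomes unclear which population the bleeding data describe.

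**Working it through.** The plan states no figure to reproduce here. The check is mainly one of logic, with a short illustration of scale.

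**1. Direction of each bleeding-related exclusion (section 4.2)**

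| Item | Who is removed | Bleeding risk of those removed |
|---|---|---|
| 1 | known bleeding diathesis | raised |
| 2 | platelets below 50,000 per microlitre | raised |
| 3 | anticoagulant or antiplatelet therapy that cannot be held | raised |
| 7 (part) | conditions requiring anticoagulation | raised |
| 8 as printed | INR below 1.5 | lower than in those kept |

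Item 8 cannot belong to the same safety policy as the other four.

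**2. Could another place correct it?** No. INR appears only in item 8.

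**3. Could the sign be an artefact of reading the PDF?** This is unlikely. In the same section, item 2 prints a less-than sign, item 6 (right ventricular systolic pressure above 50 mmHg) a greater-than sign, and the age criterion in 4.1 a greater-or-equal sign, each in the sensible direction. Only the PDF could settle it completely.

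**4. Printed rule against intended rule.** The printed rule admits INR ≥1.5. The intended rule is one of two:

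- If an inclusion-style condition was placed in the exclusion list, the intended exclusion is INR ≥1.5, which admits INR <1.5. No INR value satisfies both the printed and the intended rule.
- If the sign was simply reversed, the intended exclusion is INR >1.5, which admits INR ≤1.5. Only INR of exactly 1.5 satisfies both.

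So if the intended rule is applied, every enrolled patient meets the written exclusion, except possibly one at exactly 1.5. With 30 planned patients (section 15.1), that could be all 30.

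**5. Cost of following the printed rule.** Let *p* be the share of otherwise eligible patients with INR ≥1.5. The documents do not give *p*; the values below are assumptions.

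- Share barred = 1 − *p*
- Candidates needed for 30 places = 30 / *p*

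| *p* (assumed) | Barred | Candidates needed |
|---|---|---|
| 0.10 | 90% | 30 / 0.10 = 300 |
| 0.05 | 95% | 30 / 0.05 = 600 |
| 0.01 | 99% | 30 / 0.01 = 3,000 |

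The printed rule is impractical over this whole range, which makes enrolment in breach of it the more likely outcome.

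**6. Planned biopsies before the first scheduled safety review.** Each patient has 3 cryoprobe and 3 forceps biopsies (section 9, step 6): 3 + 3 = 6. The scheduled DSMB review follows 10 cases (section 15.1): 10 × 6 = 60 planned tissue biopsies. This counts all patients, not only those with a raised INR, so it gives context and does not measure the error.

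**The case against.** The strongest reply is that this is an obvious slip which no bronchoscopist would follow, and that other text limits the harm. Item 1 can be read to cover any known coagulopathy, and the wording of item 7 is open-ended. Patients must already have a clinical indication and be scheduled for the procedure. Needle and tissue biopsies are part of usual care. Under section 10, randomization happens only if the investigator judges further tissue biopsy appropriate. If staff apply the evident intent, the main result is a record of eligibility breaches, with few high-INR patients exposed. Reviewing eligibility at two visits does not compound the error, because the same line is read twice for the same patient. The study is also an unpowered pilot whose primary endpoint, retrieval of an adequate sample, does not involve INR.

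Much of this stands. It narrows the safety gap to a raised INR that is not recognised as a diathesis and not caught by items 3 or 7. It also makes enrolment of a patient at a dangerous INR less likely than the bare text suggests. It does not supply a numeric limit: the investigator's judgement carries no stated INR threshold, and the section 8 halt acts only after a serious bleed. Nor does it help eligibility, since applying the evident intent is exactly what produces the breaches.

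**Conclusion.** The concern holds, and the criterion must be corrected. Item 8 is wrong as written, contradicts items 1, 2, 3 and 7, and is corrected nowhere else.

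The number of patients affected cannot be derived from the documents. The 90% to 99% barred, and the 300 to 3,000 candidates, rest entirely on the assumed 1% to 10% with INR of 1.5 or more; the conclusion does not depend on that range. What follows without any assumption about INR frequency is that the printed and intended rules share no patient, except possibly at INR exactly 1.5.

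The consequences are for patient protection, valid eligibility and the makeup of the bleeding data. The primary endpoint definition, sample size, randomization and planned analysis are unaffected. The one reservation is that the sign was not checked against the PDF itself, although nothing points to a reading error.

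**What to change.** Amend section 4.2, item 8 to exclude INR ≥1.5, or INR >1.5 if the clinical team accepts a value of exactly 1.5. The clinical team should choose explicitly, because the printed text does not show which was meant.

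Bring any eligibility checklist into line. If patients have already been screened under the printed text, re-check them against the corrected criterion and document the result.

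Since section 12 lists no coagulation test, the amended item can also state that the INR comes from the usual pre-procedure examinations that section 9, step 2 already relies on.

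The cost is a one-symbol amendment, a checklist edit and a short record review. Sample size, visits and analysis do not change.

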followed by cryoprobe. In 50% of the patients cryoprobe will be followed by forceps biopsy. Randomization will take place after needle biopsy, prior to tissue biopsy. Only patients for which further tissue biopsy is deemed necessary following needle biopsy will be randomized. Remaining patients will be excluded from the study and will be treated according to the standard of care. See randomization procedure for details.

7. Cryoprobe and forceps biopsy will be performed according to standard of care and the device instructions for use. The initial freeze time for the cryobiopsy is 3 seconds as measured on the device timer. If inadequate tissue is obtained due to incomplete freeze, the freeze time can be extended by 1 second on each consecutive attempt (to a maximum of 8 seconds) at the discretion of the bronchoscopist.
8. Samples retrieved via forceps and cryoprobe biopsy will be placed into separate formalin containers and forwarded to pathology for sample processing and further pathological analysis as per standard practice.
9. Patients will be followed up for adverse events until completion of the standard of care post-procedure follow-up within 2 weeks of the procedure. The follow up may occur as a in person visit, video visit or telephone call. Adverse events will be graded using CTCAE Version 5.0 and will be attributed using the following scale:

Adverse Event Attribution Categories:

Attribution	Description
Unrelated	The AE is clearly NOT related to the intervention
Unlikely	The AE is doubtfully related to the intervention
Possible	The AE may be related to the intervention
Probable	The AE is likely related to the intervention
Definite	The AE is clearly related to the intervention

10 Randomization and Blinding

All patients will first receive needle biopsy and rapid onsite evaluation followed by tissue biopsy (forceps and cryo-biopsy). The order in which the forceps and cryo-biopsy methods are employed will be randomized 1:1. In 50% of the patients, forceps will be followed by cryoprobe. In 50% of the patients

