Review concomitant medication	X	X	
Clinical assessment/physical exam	X	X	
Urine pregnancy test (for women of child bearing potential as standard of care)	X**	X**	
Robotic-assisted bronchoscopy procedure		X	
Randomization		X	
Follow-up Chest X-ray		X*	
Adverse events	X	X	X***

*Post-procedure standard of care x-ray is done prior to discharge.

** Standard of care pre-procedure pregnancy test, on the day of the procedure if not done 30-days prior.

*** In person, video, or telephone

13 Specimen processing

For specimen processing, cryobiopsy and forceps specimens will be placed in separate formalin containers and evaluated by a dedicated pulmonary pathologist.

14 Data Collection and Confidentiality Procedures:

The following data will be collected from the patient's medical record:

1. Demographic data (such as age, gender, BMI, and other non-identifiable demographics)
2. Past medical history
3. Nodule characteristic (size, location, presence of bronchus sign, PET avidity, central lucency, distance to the pleural surface, distance to the nearest visible bronchus)
4. History of prior treatments
5. Indication for procedure
6. Radiologic data
7. Preliminary ROSE assessment (Rapid On-Site Evaluation) and final histopathology result

The following technical procedural data will be collected:

1. Position of the robotic catheter relative to the nodule prior to biopsy sampling as assessed via rEBUS ("concentric", "eccentric" or "adjacent" orientation) and/or cone beam CT.
2. Procedural details such as number of biopsies performed, duration of procedure, freezing time for cryoprobe

Study data will be collected and managed using REDCap (Research Electronic Data Capture). REDCap (www.project-redcap.org) is a secure, web-based application, with controlled access designed to support data capture for research studies. It provides: 1) an intuitive interface for validated data entry; 2) audit trails for tracking data manipulation and export procedures; 3) automated export procedures for seamless downloads to common statistical packages; and 4) procedures for importing data from external sources.

Access to the data will include the study PI and research team personnel. All protected health information (PHI) will be removed from the data when it is exported from REDCap for analysis.

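### Section 6.2 item 3 leaves passes stopped before activation out of the attempt counts, so those counts can overstate technical success

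*Combined protocol and SAP*

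**What the plan says.** All sections are in the combined protocol and SAP.

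- **6.2 item 3** asks for the numbers of successful and unsuccessful attempts and defines the unit: "One attempt is defined as insertion of the biopsy probe into the robotic sheath, activation/employment of the biopsy mechanism at the target site". To these two steps the definition adds a third: "and retrieval via the robotic sheath". An attempt succeeds if the bronchoscopist judges the retrieved tissue adequate. For unsuccessful cryobiopsy attempts, one further detail is required: whether tissue was frozen and adhered but was then lost on the way out.
- **6.2 item 1** measures "Duration of each individual biopsy procedure from first insertion of probe into robotic sheath to removal of specimen", and also a full-procedure duration that runs to the last specimen removed.
- **6.1**, the primary endpoint, is per patient: "the ability to insert the cryoprobe into the robotic working channel and retrieve at least one tissue sample per patient", with adequacy again judged by the bronchoscopist.
- **Section 3** describes the study population: "We will include patients who undergo robotic bronchoscopy with cryobiopsy". Section 4.1 requires only that robotic bronchoscopy is scheduled.
- **Section 9 item 6** states: "Randomization will take place after needle biopsy, prior to tissue biopsy". Three biopsies with each device are planned.
- **Section 14** lists "Procedural details such as number of biopsies performed, duration of procedure, freezing time for cryoprobe" among the technical data.
- **Section 15** plans descriptive statistics with 95% confidence intervals. It names no analysis set. Section 15.1 gives 30 patients and says the study is not powered for a statistical conclusion.

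**The concern.** The three parts of the attempt definition are joined, so all must occur. A pass in which the probe or forceps cannot be inserted, or is withdrawn without being activated at the target, falls outside the definition. It is not recorded as unsuccessful; it is not recorded at all.

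These are failures the pilot should be able to show. Section 2 explains the gap it fills: "This technique has not been combined with robotic bronchoscopy due to size (both length and diameter) of older generation cryoprobes". Whether the new probe can be passed and used through this robot is the question, and Section 15.1 says the data are meant to inform later studies. A count that starts only once the device has fired at the target can err in one direction only, toward success. The per-device counts could also be distorted unequally if one device stops before activation more often than the other.

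Item 1 has a related gap. A pass that yields no specimen has no end time, so its individual duration is undefined.

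**Working it through.** **Inputs from the documents.** Patients: 10 + 20 = 30, which agrees with the stated total. Planned cryobiopsies: 3 per patient, so 3 × 30 = 90. The documents give no expected failure rate, so every rate below is an assumption.

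**1. Which passes the definition covers**

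| What happens on a pass | Attempt under item 3? | Counted as |
|---|---|---|
| Not inserted | No | nothing |
| Inserted, withdrawn before activation | No | nothing |
| Activated, no adequate sample | Yes | unsuccessful |
| Activated, sample lost | Yes | unsuccessful (flagged for cryo) |
| Adequate sample | Yes | successful |

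Lost samples are expressly treated as unsuccessful attempts, so retrieval in the definition must mean retrieval of the device, not of tissue. The gap is the first two rows.

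**2. Effect on the attempt counts.** Let q be the share of passes stopped before activation and s the success rate of completed attempts. Successful over counted attempts is s; successful over all passes started is (1 − q)s; the gap is qs. Beside 90 counted attempts, 90q/(1 − q) passes go uncounted.

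| q | Uncounted passes | All passes, s = 90% | Gap (points) | All passes, s = 70% | Gap (points) |
|---|---|---|---|---|---|
| 2% | 1.8 | 88.2% | 1.8 | 68.6% | 1.4 |
| 5% | 4.7 | 85.5% | 4.5 | 66.5% | 3.5 |
| 10% | 10.0 | 81.0% | 9.0 | 63.0% | 7.0 |
| 20% | 22.5 | 72.0% | 18.0 | 56.0% | 14.0 |

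Example with q = 10% and s = 90%: item 3 shows 81/90 = 90.0%; over all passes it is 81/100 = 81.0%.

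The direction is the same if the 90 are taken as passes started. Suppose 10 fail after activation and f stop before it:

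- f = 3: 77/87 = 88.5% counted, 77/90 = 85.6% of all passes
- f = 9: 71/81 = 87.7% counted, 71/90 = 78.9% of all passes
- f = 18: 62/72 = 86.1% counted, 62/90 = 68.9% of all passes

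**3. How far 6.1 shows the same failures.** Assume independent passes.

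- If passes continue until three attempts are completed, the per-patient rate is 1 − (1 − s)³: 99.9% (s = 90%) or 97.3% (s = 70%), whatever q is.
- If there are three passes in all, it is 1 − (1 − (1 − q)s)³. For q = 2, 5, 10, 20% this is 99.8, 99.7, 99.3, 97.8% (s = 90%) and 96.9, 96.2, 94.9, 91.5% (s = 70%).

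The primary endpoint is thus an insensitive measure of failed passes, but not a blind one. If failures cluster within a patient, so that every pass fails, 6.1 shows them directly.

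**4. Why the 6.1 denominator is worth stating.** Suppose k of 30 randomized patients have no successful cryoprobe insertion or activation and all others succeed (exact 95% intervals):

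- k = 1: 29/30 = 96.7% (82.8–99.9) with all randomized; 29/29 = 100% (88.1–100) if that patient were left out
- k = 3: 27/30 = 90.0% (73.5–97.9); 27/27 = 100% (87.2–100) if those patients were left out

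**The case against.** The strongest reply is that the primary result already captures what matters. This largely stands. 6.1 does not use the attempt definition and names the ability to insert, so a patient in whom insertion fails is a primary failure. Activated passes with inadequate or lost tissue are counted under item 3. A reader might infer that failed passes vanish from the feasibility results altogether; the documents do not support that. Nor do they support saying that the primary endpoint cannot reveal such failures, as the three-pass figures show.

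A reader might also take the Section 3 sentence to remove randomized patients who never had a cryobiopsy. That reading is strained. The sentence goes on to refer to the eligibility criteria, which require only a scheduled procedure. The only exclusion stated for the day of the procedure (Sections 9 and 10) is that further biopsy is not needed or advisable, which is decided before any tissue pass. The wording is loose and no denominator is given; that calls for clarification and is not evidence of an exclusion.

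Other points are fair. Item 3 asks for counts, not a rate. If the three planned biopsies mean passes, a shortfall in attempts might be noticed. The Section 14 list is open-ended, so incomplete passes could be recorded. The full-procedure duration includes failed passes lying between the first insertion and the last specimen. Section 2 expects the 1.1 mm probe to go through the 2.0 mm channel, so insertion failures may be rare. No decision rule depends on the rate.

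None of this fills the gap in item 3: nothing requires a pass stopped before activation to be recorded, and the individual duration still has no end point without a specimen.

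**Conclusion.** The concern holds for the secondary attempt counts and the individual duration. By its own definition, item 3 omits passes stopped at insertion or before activation, and the omission can only favour success. The overstatement is qs: 9.0 points in the example with q = 10% and s = 90%, and from 1.4 to 18.0 points over the assumed range. These sizes rest on assumed rates; with no such failures the effect is zero.

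The primary endpoint stands as written, with the limitation that one later success in a patient can mask earlier failed passes. The unstated 6.1 denominator is a missing detail of lesser weight. Because the study is descriptive, the harm would be a flattering technical result carried into later planning, not a wrong decision within this trial. A pass not recorded during the procedure may be impossible to recover later, so the change should be made before data collection.

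**What to change.** 1. **6.2 item 3.** Count every pass started with either device and classify it as: not inserted; inserted but not activated at the target; activated without an adequate sample; sample lost; or adequate sample. Report adequate samples over all passes started, by device, beside the attempt counts already planned.
2. **6.2 item 1.** End the individual duration at removal of the probe or forceps, so that every inserted pass has a duration whether or not it yields a specimen.
3. **Clarification in Section 15.** State that the 6.1 denominator is all randomized patients, with failed insertion or no adequate cryo sample counted as failure. Align the Section 3 sentence with this.

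The cost is wording in Sections 3, 6.2 and 15, one outcome field per pass on the data form, and possibly lower reported rates. The number of passes, the procedure, the specimens, the sample size and the wording of 6.1 do not change.
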